## **9.0 DISCONTINUATION OF TREATMENT:**

### **9.1 Discontinuation Criteria for Individual Patients**

#### **9.1.1 Patient Withdrawal**

Patients may voluntarily withdraw consent to participate in the clinical study at any time and without giving any reason. Their withdrawal will not jeopardize their relationship with their healthcare providers or affect their future care. Patients may also choose to withdraw from study treatment, but agree to remain in the study for follow-up procedures.

### **9.1.2 Investigator Discontinuation of Patient**

The investigator may exercise medical judgment to discontinue study treatment if clinically significant changes in clinical status or laboratory values are noted.

### **9.1.3 Criteria for Protocol-Defined Required Discontinuation of Treatment**

The protocol requires discontinuation of study treatment for the following reasons:

1. Patient requests discontinuation.
2. Unacceptable toxicity that in the opinion of the investigator makes it unsafe to continue therapy.
3. Clinically significant progressive disease.
4. Investigator discretion.

### **9.1.4 Follow-Up at Treatment Discontinuation or Early Withdrawal**

Patients who discontinue treatment for any reason should complete end-of-treatment procedures when possible. End of treatment procedures will include a physical examination, CBC with differential and platelets and a limited chemistry profile (total bilirubin, serum creatinine, SGPT or SGOT). A bone marrow aspiration may be recommended only if non-response or progressive disease cannot be unequivocally diagnosed from peripheral blood. Although treatment will be discontinued at that time, all patients who do not withdraw consent for follow-up, die, or become lost to follow-up, will remain on study for follow-up evaluations. Subject will be followed for toxicity for at least 30 days after the last protocol treatment. The 30-day (+/-7 days) follow-up visit will be scheduled as a clinic visits for clinical evaluation and physical examinations. If the patient cannot make it to the MDACC clinic for this visit, the required follow up treatment procedures may be done with a local physician and the records forwarded to MDACC. The research nurse will contact the patient by telephone and get a verbal assessment of the patient's condition. The phone conversation will then be documented in the patient's charts.

## **9.2 Study Stopping Rules**

The principal investigator and MDACC IND office have the right to terminate this clinical study at any time. The principal investigator and MDACC IND office, as appropriate, will be involved in any decisions regarding terminating the study, temporarily suspending enrollment, or stopping ongoing treatment with study treatment.

Reasons for terminating the clinical study or a study site's participation include, but are not limited to, the following:

- The incidence or severity of an adverse reaction related to treatment in this study or other studies indicates a potential health hazard to patients
- Data recording is significantly inaccurate or incomplete

- Study site personnel are noncompliant with study procedures
- Pattern of noncompliance is observed

### **9.3 Protocol Violations and Deviations**

Protocol violations are defined as significant departures from protocol-required processes or procedures that affect patient safety or benefit potential, or confound assessments of safety or clinical activity. A protocol deviation is a departure from the protocol that does not meet the above criteria. Protocol violations or deviations may be grouped into the following classes:

- Enrollment criteria
- Study activities (missed evaluations or visits) except for those allowed per protocol
- Noncompliance with dose or schedule, including dose calculation, administration, interruption, reduction, or delay; or discontinuation criteria
- Investigational product handling, including storage and accountability
- Informed consent and ethical issues

## **10.0 ADVERSE EVENT REPORTING**

- 10.1** Adverse event is any untoward medical occurrence that may present during treatment with a pharmaceutical product but which does not necessarily have a causal relationship with this treatment.

Adverse drug reaction is a response to a drug which is noxious and unintended and which occurs at doses normally used in man for prophylaxis, diagnosis, or therapy of disease or for the modification of physiologic function.

Assessing causal connections between agents and disease is fundamental to the understanding of adverse drug reactions. In general, a drug may be considered a contributory cause of an adverse event if, had the drug not been administered, 1) the event would not have happened at all, 2) the event would have occurred later than it actually did, or 3) the event would have been less severe.

The Investigator or physician designee is responsible for providing source documentation and assigning attribution for all AEs.

- 10.2** Adverse Events (AEs) will be evaluated against the most current version of the selinexor and sorafenib Investigator Brochure (Appendix C and D) for expectedness. Adverse Events (AEs) will be evaluated according to the latest CTCAE version 4.03 (Appendix E) and documented in medical record. AEs will be recorded in the Case Report Form (CRF) as per appendix I. Expected events during leukemia therapy are:

### **10.2.1 Myelosuppression related events (due to disease or leukemia therapy)**

10.2.1.1 febrile or infection episodes not requiring management in the intensive care unit

10.2.1.2 epistaxis or bleeding except for catastrophic CNS or pulmonary hemorrhage

10.2.1.3 anemia, neutropenia, lymphopenia, thrombocytopenia, leukopenia

## **10.2.2 Disease related events**

10.2.2.1 symptoms associated with anemia

-fatigue

-weakness

-shortness of breath

10.2.2.2 electrolyte abnormalities (sodium, potassium, bicarbonate, CO2, magnesium)

10.2.2.3 chemistry abnormalities (LDH, phosphorus, calcium, BUN, protein, albumin, uric acid, alkaline phosphatase, glucose)

10.2.2.4 coagulation abnormalities

10.2.2.5 disease specific therapy (induction, maintenance, salvage, or stem cell therapy)

10.2.2.6 alopecia

10.2.2.7 bone, joint, or muscle pain

10.2.2.8 liver function test abnormalities associated with infection or disease progression

10.2.2.9 disease progression

10.2.2.10 abnormal hematologic values

## **10.2.3 General therapy related events**

10.2.3.1 catheter related events

10.2.3.2 renal failure related to tumor lysis syndrome or antibiotic/antifungal therapy

10.2.3.3 rash related to antibiotic use

**10.3 Abnormal hematologic values will not be recorded on the case report form. For abnormal chemical values, the apogee or nadir (whichever is appropriate) will be reported per course on the case report form, unless the event is considered a DLT as listed in section 3.4.**

#### **10.4 Serious Adverse Event Reporting (SAE)**

An adverse event (AE) or suspected adverse event is considered “serious” if, in the view of either the investigator or the sponsor, it results in any of the following outcomes:

- Death
- A life-threatening adverse drug experience – any adverse experience that places the patient, in the view of the initial reporter, at immediate risk of death from the adverse experience as it occurred. It does not include an adverse experience that might have caused death if it had occurred in a more severe form,.
- Inpatient hospitalization or prolongation of existing hospitalization
- A persistent or significant incapacity or substantial disruption of the ability to conduct normal life functions.
- A congenital anomaly/birth defect.

Important medical events that may not result in death, be life-threatening, or require hospitalization may be considered a serious adverse drug experience when, based upon appropriate medical judgment, they may jeopardize the patient or subject and may require medical or surgical intervention to prevent one of the outcomes listed in this definition. Examples of such medical events include allergic bronchospasm requiring intensive treatment in an emergency room or at home, blood dyscrasias or convulsions that do not result in inpatient hospitalization, or the development of drug dependency or drug abuse (21 CFR 312.32).

- Important medical events as defined above, may also be considered serious adverse events. Any important medical event can and should be reported as an SAE if deemed appropriate by the Principal Investigator or the IND Sponsor, IND Office.
- All events occurring during the conduct of a protocol that meet the definition of a SAE must be reported to the IRB in accordance with the timeframes and procedures outlined in “University of Texas M. D. Anderson Cancer Center Institutional Review Board Policy for Investigators on Reporting Unanticipated Adverse Events for Drugs

and Devices.” Unless stated otherwise in the protocol, all SAEs, expected or unexpected, must be reported to the IND Office, regardless of attribution (within 5 working days of knowledge of the event).

- **All life-threatening or fatal events**, that are unexpected, and related to the study drug, must have a written report submitted within **24 hours** (next working day) of knowledge of the event to the Safety Project Manager in the IND Office.
- Unless otherwise noted, the electronic SAE application (eSAE) will be utilized for safety reporting to the IND Office and MDACC IRB.
- Serious adverse events will be captured from the time of the first protocol-specific intervention, until 30 days after the last dose of drug, unless the participant withdraws consent. Serious adverse events must be followed until clinical recovery is complete and laboratory tests have returned to baseline, progression of the event has stabilized, or there has been acceptable resolution of the event.
- Additionally, any serious adverse events that occur after the 30-day time period that is related to the study treatment must be reported to the IND Office and Karyopharm Therapeutics, Inc. This may include the development of a secondary malignancy.
- All cases of selinexor or sorfenib overdose (defined as accidental or intentional ingestion of any dose of the product that is considered excessive and medically important) must be reported as an SAE to the Sponsor (MDACC IND office) and to the supporting company on the SAE Form.
- Pregnancy alone is not considered an AE. However, if a patient becomes pregnant or causes a pregnancy during treatment or within 4 weeks of ending treatment, even if the subject is withdrawn from the study, the pregnancy must be reported immediately to the sponsor (MDACC IND office) on the MD Anderson SAE Form and to the supporting company within 1 days of the Investigator’s knowledge of the pregnancy. The investigator should abide by necessary regulation for medical release from a female partner of a male subject prior to obtaining follow up. The investigator will follow the pregnancy to term or termination, will collect data on both the maternal and fetal outcome and will report all outcomes as a follow-up report to the initial pregnancy notification to the supporting company, Karyopharm Inc..  
Notwithstanding, all pregnancy outcomes that meet the regulatory definition of serious (i.e. spontaneous abortion, neonatal death,

congenital anomaly in an aborted fetus or neonate) will be reported on the MD Anderson SAE Form to the sponsor (MDACC IND office) and the supporting companies within 24 hours of Investigator knowledge of the outcome.

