### **Reproductive risks**

Patients should not become pregnant or father a baby while on this study because the drugs in this study can affect an unborn baby. Women should not breastfeed a baby while on this study. It is important patients understand the need to use birth control while on this study. It is not anticipated that female patients enrolling in this study will be able to conceive. However, in the rare event that this is possible, female patients of child-bearing potential must agree to use dual methods of contraception and have a negative serum pregnancy test at screening, and male patients must use an effective barrier method of contraception if sexually active with a female of child-bearing potential. Acceptable methods of contraception are condoms with contraceptive foam, oral, implantable or injectable contraceptives, contraceptive patch, intrauterine device, diaphragm with spermicidal gel, or a sexual partner who is surgically sterilized or post-menopausal. For both male and female patients, effective methods of contraception must be used throughout the study and for three months following the last dose.

**2.2.3** For further details of selinexor and sorafenib preclinical studies, clinical studies, toxicities, pharmacokinetics, and adverse events please see the selinexor Investigator Brochure (Appendix C) and sorafenib drug label (Appendix D).

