- 4.1.9 In the absence of rapidly progressing disease, the interval from prior treatment to time of initiation of selinexor and sorafenib administration will be at least 2 weeks for cytotoxic agents or at least 5 half-lives for cytotoxic/noncytotoxic agents. The half-life for the therapy in question will be based on published pharmacokinetic literature (abstracts, manuscripts, investigator brochure's, or drug-administration manuals) and will be documented in the protocol eligibility document. The use of chemotherapeutic or anti-leukemic agents is not permitted during the study with the following exceptions: (1) intrathecal (IT) therapy for patients with controlled CNS leukemia at the discretion of the PI and with the agreement of the Sponsor. Controlled CNS leukemia is defined by the absence of active clinical signs of CNS disease and no evidence of CNS leukemia on the most recent 2 simultaneous CSF evaluations. (2) Use of one dose of cytarabine (up to 2 g/m^2) or hydroxyurea for patients with rapidly proliferative disease is allowed before the start of study therapy and for the first four weeks on therapy. These medications will be recorded in the case-report form.
- 4.1.10 Baseline ejection fraction must be  $\geq$  40%.

- 4.1.11** Females must be surgically or biologically sterile or postmenopausal (amenorrheic for at least 12 months) or if of childbearing potential, must have a negative serum or urine pregnancy test within 72 hours before the start of the treatment.
- 4.1.12** Women of childbearing potential must agree to use an adequate method of contraception during the study and until 3 months after the last treatment. Males must be surgically or biologically sterile or agree to use an adequate method of contraception during the study until 3 months after the last treatment.

Adequate methods of contraception include:

- Total abstinence when this is in line with the preferred and usual lifestyle of the patient. Periodic abstinence (e.g., calendar, ovulation, symptothermal, post-ovulation methods) and withdrawal are not acceptable methods of contraception.
- Female sterilization (have had surgical bilateral oophorectomy with or without hysterectomy) or tubal ligation at least six weeks before taking study treatment. In case of oophorectomy alone, only when the reproductive status of the woman has been confirmed by follow up hormone level assessment

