### 10.6 Serious Adverse event Reporting to Karyopharm Inc.

All SAEs, whether related or unrelated to selinexor, pregnancies and reports of overdose regardless of suspected causality and expectedness will be reported immediately but not later than 24 hours of the PI becoming aware of the SAE to Karyopharm's SAE Management team who will ensure data is captured in Karyopharm's Pharmacovigilance system. The PI will forward completed SAE and pregnancy forms by email to [[contact]](mailto:[contact]).

Information not available at the time of the initial report (e.g., an end date for the adverse event or laboratory values received after the report) must be documented on a follow-up report. A final report to document resolution of the SAE is required.

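### Section 10.4 stops pregnancy notification to the IND sponsor, and follow-up to outcome, 4 weeks after treatment, although contraception is required for 3 months

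*Combined protocol and SAP*

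**What the plan says.** **Contraception.** Under Reproductive risks in section 2.2.2, the protocol warns that "the drugs in this study can affect an unborn baby" and states, for both sexes, that "effective methods of contraception must be used throughout the study and for three months following the last dose". Inclusion criterion 4.1.12 makes this a condition of entry: women of childbearing potential "must agree to use an adequate method of contraception during the study and until 3 months after the last treatment", and men who are not sterile must agree to the same period.

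**Pregnancy reporting to the IND sponsor.** Section 10.4 requires immediate notification to the IND sponsor, and notification to the supporting company within a day, "if a patient becomes pregnant or causes a pregnancy during treatment or within 4 weeks of ending treatment". The same provision continues: "The investigator will follow the pregnancy to term or termination". The outcomes collected are then sent to the supporting company as follow-up to the first notification.

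**Clauses that reach past 4 weeks.** Section 10.4 adds: "Notwithstanding, all pregnancy outcomes that meet the regulatory definition of serious" go to the IND sponsor and the company within 24 hours of the investigator learning of the outcome. It also says, with the IND Office and the company as recipients, that "any serious adverse events that occur after the 30-day time period that is related to the study treatment must be reported". Section 10.6 says that "pregnancies and reports of overdose regardless of suspected causality and expectedness will be reported immediately but not later than 24 hours" to the supporting company. It sets no end date and does not name the IND sponsor as a recipient.

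**The concern.** The protocol sets two limits for the same hazard. It treats conception as something to prevent for 3 months after the last dose, but it ends the sponsor notification and the follow-up duty after 4 weeks and gives no reason for the difference. A site that follows section 10.4 exactly could learn of a pregnancy conceived in, say, week 8 and would have no stated duty to notify the IND sponsor or follow the pregnancy to its end.

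Two things are at stake. The first is the sponsor's count of pregnancies. If a miscarriage or anomaly is reported from weeks 5 to 13, the IND sponsor cannot tell how many pregnancies it came from, because the notifications that would supply that number stop at week 4. The second is knowledge of the outcome. The duty to report a serious outcome begins when the investigator learns of it, and following the pregnancy is the ordinary way to learn of it. The protocol itself says, under Potential Risks, that the full safety profile of selinexor is not yet known, so the information has value even if cases are few.

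**Working it through.** No sample size, power or error rate is involved. The check compares two stated periods and then reads the other clauses against the difference.

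**Inputs.** Contraception period after the last dose: 3 months (Reproductive risks; 4.1.12), taken as 89 to 92 days depending on the calendar. Notification and follow-up period after treatment: 4 weeks, or 28 days (10.4).

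**Gap** = contraception period − 28 days. **Share** = gap ÷ contraception period.

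| 3 months taken as | Gap | Share |
|---|---|---|
| 89 days | 89 − 28 = 61 days | 61/89 = 68.5% |
| 90 days | 90 − 28 = 62 days | 62/90 = 68.9% |
| 91 days | 91 − 28 = 63 days | 63/91 = 69.2% |
| 92 days | 92 − 28 = 64 days | 64/92 = 69.6% |

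At 91 days the period is 13 weeks, and 13 − 4 = 9 weeks (weeks 5 to 13) are uncovered. The share measures calendar time only.

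**Does another clause close the gap for a pregnancy conceived in weeks 5 to 13?**

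| Clause | Initial notice to IND sponsor | Follow-up to outcome |
|---|---|---|
| 10.4, pregnancy provision | No, limited to 4 weeks | No, tied to the same provision |
| 10.4, serious outcomes | Only once a serious outcome is known | Not required |
| 10.4, late related SAEs | Only for a serious event related to treatment | For the SAE, not the pregnancy |
| 10.6 | No, the company is the recipient | Not clearly required |

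On the last entry: section 10.6 requires information that arrives after the initial report to go on a follow-up report. Since the section covers pregnancy forms, this can be read to include a pregnancy outcome. Its examples are adverse-event items, though, and its mandatory final report concerns resolution of an SAE. It tells the site to pass on what it learns, and does not plainly tell it to find out.

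**Does the follow-up schedule fill the gap?** The only dated contact after treatment that applies to all patients is the 30-day visit, plus or minus 7 days (9.1.4), so day 23 to day 37. The survival contacts in 7.2.12 are every 3 to 6 months and apply only to patients with an objective response. A non-responder has no dated contact for the rest of the contraception period.

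**After the change.** With the section 10.4 limit at 3 months after the last dose, the gap is 0 days.

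**The case against.** The strongest reply is that the two periods serve different purposes and need not match. Contraception is a precaution, while a reporting window imposes active work. Four weeks sits close to the 30-day toxicity and SAE follow-up, and the documents give no half-life or washout figure showing that conception after week 4 is exposed to drug. The supporting company, which runs the pharmacovigilance system named in section 10.6, hears of every known pregnancy with no end date. Serious outcomes and related late SAEs reach the IND sponsor in any case. The trial plans 52 patients with relapsed or refractory disease, and the protocol does not expect enrolled women to be able to conceive.

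Much of this stands, and it limits the point. Three stronger readings are tempting and should be set aside:

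- *That pregnancies in weeks 5 to 13 go unreported.* Section 10.6 contradicts this: once known, they go to the company.
- *That the IND sponsor would see serious outcomes but lose the normal ones because of the 4-week limit.* Section 10.4 sends outcome follow-up to the supporting company even inside the window. What lapses for the sponsor after week 4 is the initial notification, and with it the count of pregnancies.
- *That 69% of the fetal risk is unmonitored.* The figure is a share of days. The documents do not say that conception in weeks 5 to 13 is drug-exposed.

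What the reply does not answer is that the protocol chose 3 months as its own precaution and offers no reason for ending sponsor notification and follow-up sooner. Nor does its remark about women extend to men: section 10.4 expressly covers a male patient's partner, and the protocol makes no statement that men are unlikely to father a child.

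**Conclusion.** The point holds in a limited form. For 61 to 64 days of the 3-month contraception period, the plan does not require an uncomplicated pregnancy to be notified to the IND sponsor, and it places no clear duty on the investigator to follow that pregnancy to its outcome. The sponsor would therefore lack the number of pregnancies against which to read any serious outcome from that interval.

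This rests on two readings. The first is that the condition in section 10.4 marks the limit of the duty; the word 'only' is an inference, but no other clause imposes the duty later. The second is that the follow-up sentence in section 10.4 refers to the pregnancies just defined there.

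Severity is low. Few cases are expected, mainly in partners of male patients, and the endpoints, stopping boundaries and dose decisions are untouched. It is worth correcting because the correction is so small.

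**What to change.** In section 10.4, replace the 4-week limit with one of 3 months after the last dose of either drug, whichever is later. Naming the later drug matters because the two can be stopped at different times. Leave section 10.6 without an end date.

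At the 30-day visit in 9.1.4, tell patients to report any pregnancy, their own or a partner's, up to 3 months after the last dose. Without this the longer duty has little to act on in non-responders, who have no later dated contact. Even with it, detection after that visit depends on the patient coming forward.

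The cost is one changed phrase, one instruction at a visit already planned, and a few more pregnancies to file and follow. Sample size, monitoring rules and efficacy analysis do not change.
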